**Table 7: Start and end time of trial periods related to onset of the COVID-19 pandemic**

	Start of period	End of period (only if start date exists)
Treatment period, prior to the start of the COVID-19 pandemic	Exposure start if prior to the start of the COVID-19 pandemic else Missing	Whichever comes first of: Exposure end or Start of the COVID-19 pandemic
Treatment period, after the start of the COVID-19 pandemic	Start of the COVID-19 pandemic if between exposure start and exposure end else Exposure start if after the start of the COVID-19 pandemic else Missing	Exposure end if after the start of the COVID-19 pandemic else Missing
Safety follow-up period, prior to the start of the COVID-19 pandemic	Exposure end (plus 1 second) if prior to the start of the COVID-19 pandemic else Missing	Whichever comes first of: Date of safety follow-up visit (if existing) at time 23:59:59 else Date of last contact at time 23:59:59 or Start of the COVID-19 pandemic
Safety follow-up period, after the start of the COVID-19 pandemic	Start of the COVID-19 pandemic if between Exposure end (plus 1 second), and Date of safety follow-up visit (if existing) at time 23:59:59 else Date of last contact at time 23:59:59 else Missing	Date of safety follow-up visit (if existing) at time 23:59:59 else Date of last contact at time 23:59:59, if after the start of the COVID-19 pandemic else Missing

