### 6.7.1 Adverse Events

Adverse events (AEs) will be summarised and listed. However, the summaries will be split into the two periods, the treatment period and the safety follow-up period. This is to differentiate the AEs based on whether or not subjects are on active treatment.

The start date of the COVID-19 pandemic is defined in Section 6.8.2.

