#### Assignment of AEs to periods

An AE will be assigned to a given period (treatment or safety follow-up) if the start date of the AE is after the start date and before or at the end date of that period (see Section 6.8.2, Table 6).

For AEs with start day on the same day as the first dose was given, only AEs starting after the first dose was given will be considered treatment emergent and assigned to the treatment period.

For the handling of incomplete start dates of AEs, see Section 6.8.3.

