#### Exposure end

Date of Week 26 visit (if existing) at time 23:59:50, otherwise date of permanent discontinuation of IMP (if existing) at time 23:59:50, otherwise date of last IMP administration at time 23:59:00.

Trial ID: LP0162-1346	Date: 21-OCT-2020	Version: v1.0 Page 25 of 35
-----------------------	-------------------	--------------------------------

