### Start of the COVID-19 pandemic

The start of the COVID-19 pandemic will be set to the 1st of March 2020 at time 00:00:00 across the whole trial. The date was decided based on the fact that at this date the trial procedures were most likely not impacted by the COVID-19 pandemic but still keeping it as close as possible to the first observed occurrence of missed procedures due to the COVID-19 pandemic.

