### Trial periods

For efficacy assessments the analysis set are defined only for the treatment period which is listed in [Table 5](#) (ADaM variable APERIOD).

For safety assessments, the two analysis sets are defined by a start and end of each period which are listed in [Table 6](#) (ADaM variable APHASE).

Additionally, a sub-trial period is defined for the safety assessments considering the COVID-19 pandemic. For this we define the start and stop for the treatment and safety follow-up periods prior to and after the start of the COVID-19 pandemic which are listed in [Table 7](#).

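### SAP Table 7 gives no pandemic-split follow-up period to subjects whose exposure ended on or after 1 March 2020

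*SAP*

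**What the plan says.** SAP 6.8.2 sets the pandemic start to the 1st "of March 2020 at time 00:00:00 across the whole trial". It introduces Table 7 for the safety assessments by saying that "we define the start and stop for the treatment and safety follow-up periods prior to and after the start of the COVID-19 pandemic" and that these are the ones listed in that table.

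Table 7 has four rows. The two follow-up rows start as follows:

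- **Follow-up, before the pandemic:** one second after exposure end if that is before the pandemic start, otherwise Missing.
- **Follow-up, after the pandemic start:** "Start of the COVID-19 pandemic if between Exposure end (plus 1 second), and Date of safety follow-up visit (if existing) at time 23:59:59", with last contact replacing an absent follow-up visit, otherwise Missing.

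The post-pandemic treatment row has one branch more. If the pandemic start does not fall within exposure, it goes on to "Exposure start if after the start of the COVID-19 pandemic else Missing".

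The header of the end column is "End of period (only if start date exists"), so a Missing start removes the end as well.

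Exposure end is the "Date of Week 26 visit (if existing) at time 23:59:50, otherwise date of permanent discontinuation of IMP (if existing) at time 23:59:50", and failing both, the last IMP date at 23:59:00.

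Two other provisions create the need for the split. Protocol 14.3.13.1 requires all AEs to be shown separately before and after the pandemic start, in addition to together. SAP 6.7.1 says that "the summaries will be split into the two periods, the treatment period and the safety follow-up period".

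**The concern.** The post-pandemic follow-up row provides for subjects who were already in follow-up when the pandemic began. It does not provide for subjects who entered follow-up afterwards. For them the pandemic start lies before the window instead of inside it, and the cell returns Missing although every day of their follow-up is post-pandemic.

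Protocol 14.3.13.1 asks for the split in order to see whether home dosing and telephone or video contact affected safety monitoring. The loss is one-sided: only post-pandemic follow-up events disappear, and they come from the subjects followed entirely under pandemic conditions. Event counts in the two follow-up sub-tables would then fall short of the unsplit follow-up table. (Subject counts need not add up in any case, because one subject can have events in both parts.)

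**Working it through.** The plan states no figure to reproduce. The check applies the printed rules to dates.

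**Inputs (SAP 6.8.2)**

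- Pandemic start C = 1 Mar 2020, 00:00:00.
- Exposure end E = its calendar date at 23:59:50 (or 23:59:00 when the last IMP date is used).
- Follow-up end F = follow-up visit at 23:59:59, or last contact at 23:59:59 if there is no visit.

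**Rules as printed**

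- Pre-pandemic follow-up starts at E + 1 s if E + 1 s < C, otherwise Missing.
- Post-pandemic follow-up starts at C if E + 1 s ≤ C ≤ F, otherwise Missing.

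If E + 1 s > C, both conditions are false. Because E carries a late-evening time, this holds exactly when the calendar date of exposure end is 1 March 2020 or later. The earliest possible value on that date is 23:59:00 + 1 s = 23:59:01, already after 00:00:00. An exposure end of 29 February gives at latest 23:59:51 that evening, which is still before C.

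**Illustrative subjects**

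| Exposure end | Follow-up visit | Pre-pandemic follow-up | Post-pandemic follow-up |
|---|---|---|---|
| 5 Nov 2019 | 11 Feb 2020 | 5 Nov 23:59:51 to 11 Feb 23:59:59 | Missing (correct) |
| 10 Jan 2020 | 17 Apr 2020 | 10 Jan 23:59:51 to 1 Mar 00:00:00 | 1 Mar 00:00:00 to 17 Apr 23:59:59 |
| 29 Feb 2020 | 6 Jun 2020 | 29 Feb 23:59:51 to 1 Mar 00:00:00 | 1 Mar 00:00:00 to 6 Jun 23:59:59 |
| 1 Mar 2020 | 7 Jun 2020 | Missing | **Missing** |
| 15 Apr 2020 | 22 Jul 2020 | Missing | **Missing** |
| 15 Apr 2020 | none; last contact 1 Jun 2020 | Missing | **Missing** |

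Take the fifth subject, with 98 days of follow-up and an AE starting on 1 May 2020. Table 6 puts the event in safety follow-up. Table 7 puts it in neither part.

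**With a branch mirroring the treatment row** (otherwise E + 1 s if that is after C), the last three subjects get post-pandemic periods of 1 Mar 23:59:51 to 7 Jun 23:59:59, 15 Apr 23:59:51 to 22 Jul 23:59:59, and 15 Apr 23:59:51 to 1 Jun 23:59:59. Each equals that subject's Table 6 follow-up period. The first three rows do not change.

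**Sweep over dates.** For exposure end on each of the 235 days from 1 Mar to 21 Oct 2020 (the SAP date), with 1 to 115 days of follow-up, there are 235 × 115 = 27,025 combinations. All give Missing in both rows as printed, and all get a post-pandemic period with the branch. For exposure end from 1 Jun 2019 to 29 Feb 2020 (274 days), with 0 to 115 days of follow-up, there are 274 × 116 = 31,784 combinations, and the branch changes none. The sweep confirms the logic; it says nothing about how many subjects are affected.

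**Who is affected.** A 26-week completer has 26 × 7 = 182 days of exposure. 1 Mar 2020 − 182 days = 1 Sep 2019, so completers randomised from about that date are affected if they have follow-up in this trial. With the ±3-day Week 26 window (179 to 185 days), the boundary runs from 29 Aug to 4 Sep 2019.

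**The case against.** **The cell can be parsed another way.** The run-on clause about last contact could be taken as a fallback start date instead of a fallback upper bound. The affected subjects would then receive a post-pandemic period, so it would not be true that they get neither. But that start would be last contact at 23:59:59, which gives a zero-length period whenever last contact is the follow-up visit or there is no such visit. It would also give a post-pandemic start of 11 Feb 2020 to the first subject in the table, whose follow-up was over before the pandemic. Table 6 and Table 7's own end cells use the same phrase as an upper-bound fallback, so the reading used here is the supported one. The intended period is lost under either reading.

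**AEs may not pass through Table 7 at all.** The rule in SAP 6.7.1, "An AE will be assigned to a given period (treatment or safety follow-up) if the start date of the AE" falls within it, cites Table 6 only, and for the pandemic 6.7.1 points to 6.8.2 just for the start date. A programmer could cut the Table 6 follow-up events at 1 March and lose nothing. That is plausible, but the SAP does not instruct it, and 6.8.2 says the pre- and post-pandemic safety periods are those of Table 7.

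**The group may be nearly empty.** Subjects entering ECZTEND have essentially no follow-up here, and the rationale for Amendment 3 expected too few follow-up subjects to summarise vital signs or laboratory data. This stands as a limit on size. Against it, the extension is offered only in selected countries, subjects who stop IMP early are asked to attend a safety follow-up visit, and Protocol Appendix 9 provides for Week 26 visits during the pandemic. SAP 6.2 also plans for follow-up visits missed because of COVID-19, though that is weak support, since such a subject may have ended exposure before 1 March. An affected group is likely but not shown.

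**The omission is evident and would be noticed.** The treatment row shows what was meant, and the end cell of the defective row would itself return a date for these subjects. That supports reading this as a drafting slip. The cell nevertheless ends explicitly in Missing, and the table is written as logic to be coded.

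**Conclusion.** The point holds. As printed, Table 7 assigns neither follow-up part to any subject whose exposure ended on or after 1 March 2020, and no other section supplies the missing branch. This is a stated rule that returns a wrong result, not an unspecified detail.

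It is minor. Only the descriptive pre/post split of follow-up safety data is affected. The number of subjects and events involved cannot be obtained from the documents. The conclusion rests on two readings: that last contact is the fallback for the upper bound of the window, and that the follow-up split is built from Table 7 as 6.8.2 says.

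**What to change.** In Table 7, in the start cell of the post-pandemic follow-up row, insert a branch before the final Missing: if exposure end plus one second is later than the pandemic start, the period starts at exposure end plus one second. This mirrors the treatment row. In the same edit, bracket the upper bound (follow-up visit date if there is one, otherwise date of last contact) so that last contact cannot be taken as a start date.

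The cost is one table cell and the matching derivation. No new data are needed, and results for subjects whose exposure ended before 1 March 2020 do not change.

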### 6.8.3 Incomplete dates

#### Adverse events

If the AE start day is missing, but AE start month and year are not missing, the following rules apply:

- If the year and month of the AE start is before the year and month of the exposure start, or if the AE end date is complete and before the exposure start, the AE will not be considered treatment emergent.
- If the year and month of the AE start is the same as the year and month of the exposure start, the AE will be considered treatment emergent and assigned to the treatment period, unless the AE has a complete end date which is before exposure start.
- If the year and month of the AE start is after the year and month of exposure start, it will be assumed that the AE started on the first day of the month and the AE will be assigned to the treatment or follow-up period accordingly.

If the AE start month is missing, but AE start year is not missing, the following rules apply:

- If the year of the AE start is before the year of the exposure start, or if the AE end month and year is not missing and before the month of the exposure start and before or at the year of exposure start, or if the AE has a complete end date which is before the exposure start date, the AE will not be considered treatment emergent.
- If the year of the AE start is the same as the year of the exposure start, the AE will be considered treatment emergent and assigned to the treatment period, unless the AE end month and year is not missing and before the month of the exposure start and before or at the year of the exposure start, or the AE has a complete end date which is before the exposure start date.
- If the year of the AE start is after the year of exposure start, it will be assumed that the AE started on the 01 January and the AE will be assigned to the treatment or follow-up period accordingly.

#### Concomitant medication

For incomplete start dates of concomitant medication, the following rules apply:

- If a medication start day is missing, but start month and year is not missing, it will be assumed that the start day is the first day of the month. If the medication start day and month is missing, but start year is not missing, it will be assumed that the start day is 01 January. If the medication start day, month and year is missing, it will be assumed that the medication was started before study start. Time of medication will be set to 23:59:59.

For incomplete end dates of concomitant medication, the following rules apply:

- If a medication end day is missing, but end month and year is not missing, it will be assumed that the end day is the last day of the month. If the medication end day and month is missing, but end year is not missing, it will be assumed that the end day was 31 December. If the medication end day, month and year is missing, it will be assumed that the medication was ongoing at the end of the study. Time of medication will be set to 00:00:00, unless the end date is equal to the start date of the concomitant medication where the time of the end date will be set to 23:59:59.

Administration of IMP

In case of incomplete time registrations of IMP dosings with dates of administration being available, the time of 12:00:00 will be used.

**6.8.4 Early termination and unscheduled visits**

When no data is available from a certain scheduled post-baseline visit for a subject, data from early termination visits and unscheduled visits have the potential to replace data from that particular scheduled visit in data summaries, provided that the data is collected between 6 days before and 7 days after the planned time point for the scheduled visit, as displayed below.

**Table 8: Visit days and windows**

Visit (Target day)	Visit window (Day is date of assessment minus date of first dose)
Week 2 (Day 14)	Day 8 to 21
Week x (Day 7*x) (where x= 4, 6, ..., 26)	Day 7*x-6 to 7*x+7
Safety follow-up	106-119 days after last dose

When data from both unscheduled and early termination visits exist within the given visit window, the early termination visit will be selected for analysis. When no data from early termination visit and data from unscheduled visit(s) exist, within window, the unscheduled visit will be selected for analysis. If several unscheduled visits exist, the one closest to the target day will be selected for analysis. If the distance to the target day is tied, the latest unscheduled visit will be selected.

### 6.8.5 Technical handling of intercurrent events and missing values

Intercurrent events and missing values will be handled as described in the protocol.

This section describes the technical aspects in relation to this.

The variable DTYPE is created to indicate each special handling of data used. Observed data will be indicated when DTYPE is empty (DTYPE=''). Subjects having experienced a prior intercurrent event or having a missing value at a visit can have inserted 5 extra data rows of separate DTYPEs. These data rows will be inserted dependent on the needs of the estimands applied. Non-responder imputation will be indicated using DTYPE='NRI', no value will be imputed but criteria/outcome values will be imputed as non-response. Worst observation carried forward will be indicated using DTYPE='WOCF', imputing the worst observation observed up until and including the data point. When imputing values, DTYPE='MISSING' will be used on relevant missing or set to missing data. In addition, to indicate when there is no observed value an extra category DTYPE='MISSOBS' is created. DTYPE='LOCF', last observation carried forward (including baseline observation) is used in the special case when no assessments exist at the first scheduled post-baseline assessment visit prior to any intercurrent events.

As intercurrent events are handled based on whichever of the regarded prior intercurrent events comes first, 3 first prior intercurrent event indicator variables are created. ICECOVIN indicates which of three prior intercurrent events comes first: permanent discontinuation of IMP not due to the COVID-19 pandemic, rescue treatment not due to the COVID-19 pandemic, or subject-onset of the COVID-19 pandemic. ICECOVIN is used in the COVID-19 modified composite and hypothetical estimands. ICECOMIN indicates which of either rescue treatment or permanent discontinuation of IMP comes first including events due to the COVID-19 pandemic. ICECOMIN is used in the composite estimand. ICETREIN indicates which of either permanent discontinuation of IMP not due to the COVID-19 pandemic or

Trial ID: LP0162-1346	Date: 21-OCT-2020	Version: v1.0 Page 30 of 35
-----------------------	--------------------------	--------------------------------

subject-onset of the COVID-19 pandemic comes first. ICETREIN is used in the treatment policy estimands.

Missing values due to the COVID-19 pandemic will be handled using the flag MISSCVFL which will only be assigned onto visits with no observed data.

As a convenience, estimand flags have been created for each estimand in order to select the correct data rows based on the intercurrent event indicator variables and the DTYPE variable. How data rows are selected for the primary analysis of each estimand can be seen in [Table 9](#).

Trial ID: LP0162-1346	Date: 21-OCT-2020	Version: v1.0 Page 31 of 35
-----------------------	-------------------	--------------------------------

**Table 9: Technical handling of intercurrent events and missing data in the primary analysis of the estimands**

Estimand flag	Binary endpoints				Continuous endpoints				
	EBICOVFL	EBICOMFL	EBITREFL	EBIHVFL	ECOHVFL	ECOTREFL	ECOCOVFL	ICECOVIN	ICETREIN
First prior intercurrent event indicator variable	ICECOVIN	ICECOMIN	ICETREIN	ICECOVIN	ICECOVIN	ICECOVIN	ICECOVIN	ICECOVIN	ICECOVIN
First prior intercurrent event (indicator)	COVID-19 modified composite	Composite	treatment policy	hypothetical	hypothetical 	treatment policy	COVID-19 modified composite	hypothetical 	treatment policy
Rescue treatment (RESCUEFL or RESCUEFL) 	DTYPE=NRI	DTYPE=NRI	NA	DTYPE=	DTYPE=	NA	DTYPE=	DTYPE=	DTYPE=
Observed data	DTYPE=NRI	DTYPE=NRI	NA	MISSING	MISSING	WOCF	WOCF	MISSING	WOCF
Missing data	DTYPE=NRI	DTYPE=NRI	DTYPE=	DTYPE=	DTYPE=	DTYPE=	DTYPE=	DTYPE=	DTYPE=
Permanent discontinuation of IMP (DISCNFL or DISCNFL) 	DTYPE=NRI	DTYPE=NRI	DTYPE=	MISSING	MISSING	MISSING	MISSING	MISSING	MISSING
Observed data	DTYPE=NRI	DTYPE=NRI	DTYPE=	DTYPE=	DTYPE=	DTYPE=	DTYPE=	DTYPE=	DTYPE=
Missing data	DTYPE=	NA	DTYPE=	DTYPE=	DTYPE=	DTYPE=	DTYPE=	DTYPE=	DTYPE=
Subject-onset of the COVID-19 pandemic (SOC19FL)	MISSING	NA	MISSING	MISSING	MISSING	MISSING	MISSING	MISSING	MISSING
Observed data	DTYPE=	NA	DTYPE=	DTYPE=	DTYPE=	DTYPE=	DTYPE=	DTYPE=	DTYPE=
Missing data	MISSING	NA	MISSING	MISSING	MISSING	MISSING	MISSING	MISSING	MISSING
No prior intercurrent event (*)	DTYPE=NRI	DTYPE=NRI	DTYPE=	DTYPE=	DTYPE=	DTYPE=	DTYPE=	DTYPE=	DTYPE=
Missing data not due to the COVID-19 pandemic	DTYPE=NRI	DTYPE=NRI	DTYPE=	DTYPE=	DTYPE=	DTYPE=	DTYPE=	DTYPE=	DTYPE=
Missing data due to the COVID-19 pandemic	MISSING	MISSING	MISSING	MISSING	MISSING	MISSING	MISSING	MISSING	MISSING
Observed data	DTYPE=	DTYPE=	DTYPE=	DTYPE=	DTYPE=	DTYPE=	DTYPE=	DTYPE=	DTYPE=

**Abbreviations:** NA = Not applicable; COVID-19 = Coronavirus Disease 2019; IMP = investigational medicinal product; RESCNCFL = rescue treatment not due to the COVID-19 pandemic flag; RESCUEFL = rescue treatment flag; DISCNFL = permanent discontinuation of IMP not due to the COVID-19 pandemic; DISCONFL = permanent discontinuation of IMP; SOC19FL = subject-onset of the COVID-19 pandemic.

- 1) Which first prior intercurrent event indicator is used is dependent on the estimand.
- 2) If no post-baseline scheduled assessment exists, the last observation is carried forward (including baseline) with DTYPE='LOCF'.

### 6.8.6 Timing of intercurrent events

Actions taken based on intercurrent events will be dependent on whether or not an intercurrent event happens prior to a relevant visit. The rule will be that if any regarded intercurrent event happens prior to the date of the visit then the intercurrent event will be defined to be prior to the relevant visit. The following list of dates will be used in a prioritised manner as the date of the visit, i.e. if a date higher in the hierarchy exists that date will be used:

1. Observed date of the visit. When no data is available from the scheduled visit, data and visit date can be mapped to the visit per the rules stated in Section 6.8.4.
2. Planned date of the visit – 7 days, to account for the visit window.

In case intercurrent events occurs on the same date the following prioritise list will be used: rescue treatment, permanent discontinuation of IMP, and then subject-onset of the COVID-19 pandemic.

